### ***Aim 2 mSupport Pilot Study with Health Care Providers***

Using similar methods described above for the cognitive interviews with nurses, HCC multi-disciplinary health care providers who provide care for HNC (N=10) will be recruited to participate in individual or small group discussions to pilot test the mSupport tool. Providers in various HNC clinics (i.e., surgery, radiation oncology, medical oncology, maxillofacial prosthodontics, speech pathology, dietetics, behavioral medicine) with at least 3 providers from the community setting who provide care for HNC patients will be recruited. All providers will have been practicing for at least 6 months.

#### **Number of Subjects**

Study Activity	Number of Subjects
HNC Dyad Key Informant Interviews	15 patients and 15 caregivers (N=30)
Oncology Dietitian Surveys	N=35 dietitians
Cognitive Interviews	2 patients, 2 caregivers, 2 nurses (N=6)
mSupport Pilot Testing	33 patients and 33 caregivers (N=66)

mSupport Pilot Study with Health Care Providers	N=10
Total	147

**Setting**

- Hollings Cancer Center at MUSC
- The panel of dietitians will be recruited through the Oncology Nutrition Dietetic Practice Group listserv.

**Recruitment Methods and Consent Process**

**Phase I Key Informant Interviews.** We will conduct key informant interviews with patients and their caregivers in person in a private interview room. As in our previous studies, research staff will review clinic rosters to identify potentially eligible patients who meet study criteria and are scheduled for a follow-up care appointment at the Hollings Cancer Center. These potential participants will be approached in the clinic or mailed a study recruitment letter and provided with written study information. After reviewing the study and answering any questions, we will schedule interviews with those who are eligible and interested in participating in the study.

During recruitment, patients will be asked to select their primary caregivers (i.e., spouse, family member, friend), or the individual on whom they rely primarily for support; if patients are unable to identify a supporter, they may still participate in the study. All potential patients and caregivers will be allowed to discuss the study individually or in pairs based on their preferences. If caregivers are present in the clinic, study staff will provide the caregiver the opportunity to ask questions if interested in participating in the study. If the caregiver is not present, patients will be asked to consult with their nominated caregiver before providing caregiver contact information to study staff for invitation to participate in the study. Once caregiver contact information is obtained, research staff will attempt to contact the caregiver by ground mail or telephone. If a home address is obtained for the caregiver, a letter will be mailed to the caregiver. An information letter will describe the study in more detail and will ask the caregiver to contact study staff to answer any questions they may have. Similarly, if the caregiver is contacted by telephone, the study staff will describe the study in more detail and answer any questions. If we do not receive a response from the caregiver, we will then follow up the mailing with no more than ten attempted phone calls at different times. We will leave no more than two messages. A copy of all recruitment correspondence will be kept on file.

Informed consent and HIPAA forms will be signed in person before the interview is conducted after individuals have time to read over the consent on their own and the research staff describe the elements of the study and answer any questions. All participants will receive copies of consent and HIPAA forms for their records. The Principal Investigator, trained Study Coordinator, Research Assistant and health care providers on our study team will administer consents. Participants (patients and caregivers) will receive \$25 gift cards to Walmart and parking vouchers.

**Phase I Oncology Dietitian Surveys.** Participants (N=35) will be recruited through the Oncology Nutrition Dietetic Practice Group (<https://www.oncologynutrition.org/>) of the Academy of Nutrition and Dietetics listserv. Volunteers will be contacted by email and linked to a web-based 20-minute REDCap (Research Electronic Data Capture), survey. A waiver of written or signed consent has been requested and participation in the interview will indicate implied consent. Participants will be enrolled in a gift card lottery for a \$25 Amazon gift card to thank them for efforts.

**Phase I Cognitive Interviews.** Using similar criteria and methods described above for key informant interviews, we will recruit HNC patients, caregivers and clinic nurses to participate in cognitive interviews to pretest the mSupport tool. We will recruit individuals who completed their primary treatment (i.e., any combination of surgery, chemotherapy, and/or radiation therapy) within the past 24 months and conduct a screening interview with each enrolling patient to select his or her primary caregiver. We will recruit 2 patients, 2 caregivers and 2 nurses to participate in the cognitive interviews. Patients and caregivers will receive a \$25

gift card to Walmart and parking voucher to thank them for their time and effort in the study. Nurses will receive a \$25 gift card to Target to thank them for their time.

Informed consent and HIPAA forms will be signed in person before the interview is conducted after the research staff describe the elements of the study and answer any questions for patients and caregivers. All participants will receive copies of consent and HIPAA forms for their records. The Principal Investigator, trained Study Coordinator, Research Assistant and health care providers on our study team will administer consents. Participants (patients and caregivers) will receive \$25 gift cards to Walmart and parking vouchers. A waiver of written or signed consent has been requested for the cognitive interviews with clinic nurses; information about the study will be provided prior to scheduling and beginning the small group discussion and participation will indicate implied consent.

**Phase II mSupport Pilot Study with Patients and Caregivers.** As in our previous studies, research staff will review clinic rosters to identify potentially eligible patients who meet study inclusion and exclusion criteria. These potential participants may be approached in the clinic (if safe and feasible based on clinic requirements during the COVID-19 pandemic) or provided written study information via a flyer or mailed study recruitment letter. Staff will follow-up with potential participants either by phone or email to review the study and answer any questions.

If eligible and interested, study staff will use the REDCap combined e-consent/HIPAA template to conduct the informed consent process. Informed consent and HIPAA forms will be signed after individuals have time to read over the consent on their own and the research staff describe the elements of the study and answer any questions.

- If a participant is being enrolled virtually, the participant and study staff will access the consent form online. Participants will walk through the study purpose, procedures, risks and benefits and have the opportunity to ask questions. Participants will electronically sign forms, study staff will also electronically sign the forms, and participants will receive copies of consent and HIPAA forms for their records by mail/email.
- If a participant is recruited in-person, study staff will follow a similar process. Using a tablet, the participant and study staff will access the consent form online. Participants will walk through the study purpose, procedures, risks and benefits and have the opportunity to ask questions. Participants will electronically sign forms, study staff will also electronically sign the forms, and participants will receive copies of consent and HIPAA forms for their records by mail/email.

The Principal Investigator, trained Study Coordinator, Research Assistant and health care providers on our study team will administer consents. These procedures will be done on our research team's laptop and/or tablet, but no data will be stored on either device; all data will be stored securely in REDCap.

If technology challenges arise, study staff may also use a combined consent/HIPAA hard copy form (printed from REDCap), either in-person or sent through the mail. During the consent/assent phone call, research staff will ensure all questions are answered. The participant will sign and date the forms and return to the study staff. Study staff will sign and date the forms and will mail/email a copy to the participant. No study activities will be conducted until both the participant and study staff have signed and dated the informed consent/HIPAA documents.

After enrollment, participants will be given the option to complete the baseline/needs assessment survey by telephone, mail, or online. After this survey is complete, study staff will schedule either: an in-person clinic session (if safe and feasible based on clinic requirements during the COVID-19 pandemic); or a virtual session. Either will be conveniently timed for participants schedule. In either scenario, participants will receive and review a tailored care plan, which includes messages, referrals and educational materials. In-person study activities will take place in a private clinic office or conference room in a location that is convenient for the participants and will conform to university COVID-19 safety recommendations. The virtual visit will be conducted via telephone or doxy.me with care plans being provided electronically or by mail.

Based on the caregiver's preference (either within the session or at a later date), he/she will receive an overview of the mobile app and links to training videos. After the study session, study staff will prepare the final care plan with referrals and educational materials and mail a study packet with gift cards to participants. Six-eight weeks later, participants will complete follow-up surveys by telephone, mail or email. Both the patient and caregiver participants will receive \$50 (two \$25 gift cards) after completing the initial survey and clinic/virtual session (\$25) and the follow-up survey (\$25).

### Study Design / Methods

#### Aim 1 Methods

**HNC Dyad Key Informant Interviews.** We will conduct dyadic interviews with HNC survivors and caregivers. Using a structured interview guide, we will explore post-treatment nutritional expectations, challenges, nutritional support task demands, interactions between survivors, caregivers and providers and experiences returning home after treatment. We will ask about survivor and caregiver nutritional recovery expectations and emotional and practical nutritional caregiving challenges faced. After a demonstration of the mSupport tool, care plan, and viewing of example messages and a peer support video on a mobile device, participants will provide feedback about the format, content and delivery and offer improvement recommendations. We will continue to conduct interviews until we reach saturation in themes. All interview participants will be asked to complete a short demographic survey (<5 minutes) to characterize group participants. In addition, information about each patient's medical history will be obtained from the electronic medical record. Interviews will last approximately 30 to 45 minutes.

[name] will moderate the 30-45 minute audio-taped interviews using a structured interview guide to explore post-treatment nutritional expectations, challenges, interactions between survivors, caregivers and providers and experiences returning home after treatment. We will ask about survivor and caregiver nutritional recovery expectations and emotional and practical nutritional caregiving challenges, including nutritional support task demands. After demonstrating the mSupport tool, care plan, and viewing messages and a peer support video on a mobile device, participants will provide feedback and offer recommendations. We will continue to conduct interviews until we reach theme saturation.

**Oncology Dietitian Surveys.** Building on findings from initial dyad interviews, a cross-sectional survey will be refined with guidance from our Clinical Advisory Board, cognitively pretested and administered to a panel of dietitians. We will assess key caregiver nutritional support tasks and perceptions of caregiver nutritional support demands, psychosocial concerns and barriers (Table 1). Participants will view/rate a mock care plan and video, offering suggestions to improve content.

**Table 1. Survey Measures for Oncology Dietitian Experts (Aim 1)**

Domain	Description/Rationale
Primary nutritional support tasks	
 
Ratings of importance (Not at All to Extremely), perceived task demand difficulty (Not at All to Extremely), and clarity of wording (Poor to Excellent) of key HNC nutritional caregiving support tasks and healthcare barriers.
 

Resource priority	
 
Ranking of key caregiver resources identified to support HNC nutritional needs (adapted from our prior work).
 

Barriers to meet caregiver needs	
 
Barriers to meeting needs of caregivers (e.g., time, specialized training, leadership support) in a variety of care settings will be assessed using a tool designed by our team in prior research (see Preliminary Data).
 

Acceptability	
 
After review of mock care plan, messages and video, participants will complete ratings concerning acceptability adapted from our prior SNAP measures (Not at All Satisfied to Extremely Satisfied).
 

Demographics	
 
Specialty, patient volume, years in practice, age, gender, race/ethnicity.
 

**Aim 1 Data Management and Analysis.** Interviews will be transcribed and analyzed using rigorous content analysis methods for systematic theme identification. Themes will be compared within/across survivor-caregiver groups. Transcripts will be coded by [name] and study staff and regrouped and reorganized until investigators agree on categories. This initial theme identification process will be followed by team meetings to finalize themes and implications for the intervention design. Expert survey responses will be summarized and guide the content, format and delivery of the mSupport system.

**Intervention Development.** Building on Aim 1 interview/survey findings, final needs assessment domains that

can appropriately be addressed through mobile support will be developed along with associated messages and tips by our Clinical Advisory Board. Brief (3-6) minute peer videos of volunteer HNC dyads and nurses will be developed by the MUSC Office of Instructional Technology to share encouragement, support and meal preparation tips. Table 2 outlines caregiving skills from the transactional model mapped to HNC recovery domains and example tailored mSupport elements. The finalized system will undergo pretesting with dyads (N=2, \$25 gift card) and nurses (N=2, \$25 gift card) to gather feedback on content, layout and assessment experiences. A convenience sample of dyads will complete the mSupport protocol and a cognitive pretesting guide will be used to examine users' experiences. After a demonstration, nurses will provide feedback about clinic feasibility. Findings will guide the team to finalize the system.

**Table 2. Caregiving Processes Mapped to HNC Support Tasks: Preliminary Intervention Guide**

Caregiving Process	Caregiver Nutritional Support Domain Examples	mSupport Intervention Elements
Monitor Interpret	Tracking nutritional intake and problems with swallowing, dry mouth and distress (attend to frequency, changes, patterns)	Alerts to monitor symptoms/when to call provider, support/reinforcement messages
Make decisions Adjustments	Weighing competing demands, adjusting food timing/amount, considering support consequences, planning ahead	Encouragement through tips and peer videos
Access resources	Seeking/coordinating needed nutritional support resources	mSupport reminders/prompts
Hands-on care	Food preparation, wound care, encouragement	Symptom management tips, peer videos
Work together with ill person	Planning together, achieving shared understanding of recovery preferences, constructive communication	Clinic discussion, teamwork tips provided through peer videos
Navigate health system	Evaluating/seeking nutritional care, advocating for survivor	Care plan content, provider video

AThese domains will be refined by Clinical Advisory Board in Aim 1

**Technology Development.** Our Software Systems Developers from the MUSC Technology Applications Center for Healthy Living (TACHL) developed the SNAP tool and care plan template. The HIPAA and FERPA-compliant SNAP tool is an Enterprise Data Management System with a data collection application and personalized care report delivery component. The web-based interfaces feed into REDCap a secure application supporting validated data entry, audits, import/export procedures and branching logic. A wireless touchscreen tablet device renders a web-based interface designed for ease of data collection with color displays, large font, pictures, and skip patterns. The system authenticates to a data tracking system, registers assessments, records data and, based on administrator-designated logic, generates a tailored care plan with a care summary page followed by tailored messages, referrals and listing of educational materials mapped to reported concerns, symptoms and behaviors of patients and caregivers. Capitalizing on our current SNAP Tool, in this study we will tailor the system to focus on nutrition and enhance the tool to incorporate mSupport (see Figure 2 above). The IT development phase will include needs assessment customization, mSupport App interface design, and testing. Future deployment will be supported by SNAP's web-based access for easy community dissemination.

The mobile intervention will support caregivers at home and reinforce caregiving skills discussed at the clinic. mSupport will include 4 weeks of bi-weekly monitoring of survivor nutrition status and caregiver distress, needs and perceptions of survivors' nutrition status. Based on timing preferences, a schedule of prompts will be delivered to each dyad; based on real-time responses to nutritional status and distress items, tailored links to App resources will follow. mSupport will provide a platform for real-time assessment of nutritional challenges and will address needs through coaching with support messages and videos. Survivor-caregiver communication will be facilitated by prompting symptom management discussion. Guided by our Clinical Advisory Board, the system will be optimized to assess/address actionable support needs that can be linked to mobile support resources; this will set the stage for cost-effective future dissemination. For tracking purposes and to assure connection with the study Social Worker if needed, participants will be queried weekly for unmet needs.

## Aim 2 Methods

**mSupport System Pilot Testing.** Patients and caregivers will complete a 30 minute baseline and needs assessment survey by telephone, mail or online. They will then be scheduled for either an in-person or virtual (via doxy.me or telephone) visit at a convenient time. We will then deliver the intervention in a 30-45 minute in-person or virtual session. The intervention includes several activities, including a care plan discussion with a

Nurse Practitioner (in person, telephone or using doxy.me), and app training for caregivers, which will be accomplished with a series of short training videos. App training will be followed by 4 weeks of App use with bi-weekly real-time prompts and feedback for caregivers. Approximately 6-8 weeks later, patients and caregivers will complete 30 minute follow-up surveys. Due to the COVID-19 pandemic, the majority of study events will be offered to patients in multiple formats based on preference and safety protocols in the clinic.

For convenience and safety, study activities may be split up over time to accommodate participant scheduling preferences. And though some sessions will take place at the clinic, we may deliver some activities by telephone, doxy.me or in an alternate location. Specially, because many HNC families reside in the American Cancer Society Hope Lodge during radiation therapy, we may conduct research activities in a private conference room in this location. In in-person or virtual scenarios, a tailored care plan will be generated and reviewed with our Nurse Investigator.

Within the virtual or in-person session or at later date based on preference, caregivers will receive training on mSupport technology through a series of short training videos. Caregivers will then be prompted twice a week for 4 weeks to report symptoms, nutritional status and distress with algorithm-driven links to 3 support sources, including messages, tips and peer videos (see Table 2 above). We may contact caregivers by phone weekly to ensure that there are no technical issues with the app. Participants will also complete a 10-15 minute follow-up interview by telephone, mail or email six to eight weeks following the clinic session to gather self-reported data about unmet needs, whether and how the care plan and referrals were used after the clinic session, satisfaction with the session, care plan, and mSupport program and preferences concerning the timing and content of the clinic session and delivery of the mSupport program.

In order to collect feedback on care plan discussions and to further refine methods and processes for future studies, we would like to conduct in-depth interviews with nurse practitioners who participate in the pilot study visits. (N=2, \$100 gift card)

Lastly, after completing the pilot, we will conduct 45-minute audiotaped individual/small group interviews with 8 HNC health care providers (a surgeon, medical oncologist, radiation oncologist, nurses, dental, speech, and nutrition specialists, and community providers) to evaluate feasibility and recommendations for future system extension for broader reach in other care settings. (N=8, \$25)

**Aim 2 Data Management and Analysis.** Descriptive statistics across and within dyads will characterize patient and caregiver needs and system acceptability. Preferences by race, sex, stage and cancer site will be explored using descriptive statistics and graphics (bar charts, plots) to highlight future intervention directions. To explore potential effect sizes for future research, average change in future trial outcome variables from baseline to follow-up will be estimated and 95% confidence intervals calculated. Content analysis will be used to examine themes in open-ended responses provided by dyads (with differences explored by sex) and providers. Finally, tracking records will be reviewed to assess program delivery, adherence and preferences (Table 3).

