### Intervention to Be Studied

As highlighted above in Figure 1, this 2-phase study will develop (phase 1) and pilot-test (phase II) a mobile-Support program for HNC survivors and their caregivers. The resulting system will include three elements to: 1) systematically administer survivor/caregiver nutritional needs assessments at the end of treatment, 2) generate tailored caregiver-focused nutritional care plans and 3) provide bi-weekly mobile support (encouragement, reminders and tips delivered through messaging and peer videos) to caregivers as they manage nutritional needs and concerns during the initial recovery period (see Figure 2).

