**Figure 2. Data Flow [Existing SNAP, New Development]**

## Study Endpoints Overview

This study involves two phases. In the first phase, we will conduct 15 key informant interviews with HNC patients and their primary caregivers and administer surveys to an expert panel of oncology dietitians (N=35). We will also conduct cognitive interviews to pretest our mSupport program with 2 patients and their caregivers (N=4) and 2 nurses. In the second phase of this study, after patients and caregivers complete a baseline survey, we will implement and test the delivery of the mSupport system in the HCC clinic with 33 patients and their primary caregivers (N=66) and follow with 4 weeks of mobile monitoring and support. Participants will complete a follow-up interview 6 weeks following the clinic session. Finally, we will hold individual or small group interviews with health care providers (N=10) to pilot test the mSupport system.

The sections that follow are organized by study phase. As described in detail below, all patients and their caregivers will be recruited through the HCC Multi-Disciplinary Head and Neck Tumor Program. Patient and caregiver data will be collected by self-report in key informant interviews, in-person clinic interviews and telephone, mailed or emailed follow-up interviews. In addition, we will collect patient clinical data from the electronic medical record. Multi-disciplinary health care specialists involved in the care of HNC patients will be recruited at the HCC and around the state of South Carolina and provide data in web-based surveys and interviews.

[figure not shown]

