**Figure 3. Conceptual Model of the Intervention**

## Inclusion and Exclusion Criteria/Study Population

### Aim 1 Key Informant Interviews

Men and women from all racial/ethnic backgrounds with stage I-IVA HNC receiving care at the HCC Multi-Disciplinary Head and Neck Tumor Program will be identified and mailed a letter or approached by study staff at routine follow-up appointments using standardized recruitment protocols. We will recruit

individuals who completed their primary treatment (i.e., any combination of surgery, chemotherapy, and/or radiation therapy) between 6-24 months prior to the interviews and who report having experienced nutritional challenges at the end of treatment. This timeframe will permit recovery time after treatment but will allow adequate recall for participants to reflect about their experiences at the end of treatment. Patient inclusion and exclusion criteria are listed below.

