### ***Aim 2 mSupport Pilot Study with Patients and Caregivers***

Using similar methods described above for key informant interviews, we will recruit HNC patients and their caregivers to participate in phase II. HNC patients (see inclusion and exclusion criteria listed below) who are in the last several weeks of treatment or completed their primary treatment (i.e., any combination of surgery, chemotherapy, and/or radiation therapy) within the past 3 months who own and use smartphones will be recruited and a screening interview will be conducted for the selection of a caregiver.

Patient Inclusion Criteria:

- 18 years and older
- Patients with stage I-IVB HNC of the upper aerodigestive tract (including lip/oral cavity, nasopharynx, salivary gland, oropharynx, hypopharynx, paranasal sinus, and larynx cancers) and cutaneous cancers of the head and neck region
- In the last several weeks of treatment to 3 months following completion of primary treatment (i.e., any combination of surgery, chemotherapy and radiation therapy)
- Experienced nutritional challenges at the end of treatment as assessed in a 6-item screener

Patient Exclusion Criteria:

- HNC patients who do not undergo treatment
- Patients who do not read or understand English
- Patients who are cognitively impaired and cannot complete interviews, as judged by the referring health care provider

Caregiver Inclusion Criteria:

- 18 years and older
- Provide care for a loved one with stage I-IVA HNC who has completed treatment

Caregiver Exclusion Criteria:

- Caregivers who do not read or understand English
- Caregivers who are cognitively impaired and cannot complete interviews, as judged by the referring health care provider
- Do not have a smartphone for use in the study

We will recruit 33 patients and their 33 caregivers to participate in the pilot study. To accommodate attrition during pilot testing, we will over-recruit by 3 (10%). The dyads will be diverse by race, cancer site and nutritional challenges (i.e., feeding tube status). The average number of newly diagnosed HNC patients per year at HCC in 2013-2014 was approximately 200 (~16/month) which will allow us to feasibly achieve our desired sample size. As 70% of HNC patients are male, we will oversample women (40%) to assure ability to explore experiences in female patients.

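### The single-arm pilot labels uncontrolled baseline-to-follow-up change as exploring effect sizes; it should be reported as within-group change, alongside SDs, correlations and retention

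*Combined protocol and SAP*

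**What the plan says.** The Aim 2 Data Management and Analysis paragraph (under Aim 2 Methods) states the purpose and the estimate together: "To explore potential effect sizes for future research, average change in future trial outcome variables from baseline to follow-up will be estimated", with 95% confidence intervals. No hypothesis test is planned.

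The design around that sentence is as follows.

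- **One group.** Study Endpoints Overview and the Aim 2 recruitment section describe 33 patients and 33 caregivers, all of whom receive mSupport. No comparison group is described. Over-recruitment by 3 for attrition implies about 30 completing dyads.
- **Entry window.** Patients are eligible "In the last several weeks of treatment to 3 months following completion of primary treatment".
- **Selection.** Patients must have "Experienced nutritional challenges at the end of treatment as assessed in a 6-item screener". The cut-off is not given.
- **Follow-up.** One sentence in Aim 2 Methods places the follow-up interview "six to eight weeks following the clinic session to gather self-reported data about unmet needs". Another says "Approximately 6-8 weeks later, patients and caregivers will complete 30 minute follow-up surveys", straight after describing the 4 weeks of App use.
- **Purpose of the support.** Intervention to Be Studied says it goes "to caregivers as they manage nutritional needs and concerns during the initial recovery period".
- **Use.** Under Specific Aim 2, the results are to feed a larger multi-site trial.

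Phase 2 Outcomes describes the same analysis more neutrally, as looking at changes over time, and lists it after feasibility and acceptability.

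**The concern.** An effect size for a controlled trial is a difference between arms. A pre-post mean in a treated group is that difference plus whatever would have happened anyway, and here there is reason to expect that something would have happened. Patients are enrolled at or shortly after the end of treatment, and the support is aimed at early recovery. The Preliminary Data section reports that 77% of providers saw the greatest difficulty right after treatment. When Aim 1 needs people who have had time to recover, it waits at least 6 months: "This timeframe will permit recovery time after treatment".

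For patient nutrition and symptom outcomes, selection on nutritional problems may add regression to the mean. How much cannot be said, since the screener asks about the end of treatment and its threshold is not stated.

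The bias could go either way. Patients enrolled during late treatment may worsen before they improve, which would hide an effect. Those enrolled later may simply recover, which would inflate one. For caregiver outcomes the documents give no natural course at all.

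No caveat about natural course appears anywhere. A figure labelled an effect size, with a 95% interval beside it, is easily carried into the planning of the next trial as though it were the between-arm quantity.

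**Working it through.** **The plan's own figure.** The only related number is the pilot size. Over-recruiting 30 by 10% gives 30 × 1.10 = 33, as stated. No SD, effect size, power or target precision is given, so there is no further figure to reproduce.

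**Timing against recovery.**

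- 3 months = 13.0 weeks. Adding 6 to 8 weeks puts the latest entrants' follow-up at about 19 to 21 weeks after treatment, plus any wait for the session.
- If the 6 to 8 weeks are counted from the end of App use, the maximum is 13 + 4 + 8 = 25 weeks.
- The Aim 1 minimum of 6 months is 26.1 weeks.

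On either reading, and leaving aside any wait for the session, follow-up ends before the time Aim 1 allows for recovery.

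**What the interval covers.** Let δ be the intervention effect and m the natural change, both in outcome SDs. The pilot estimates δ + m. Take equal SDs at both times, correlation r, and approximately normal change:

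- SD of change = √(2(1 − r))
- Noncentrality = m / (SD of change / √n)
- Chance that the interval contains δ = P(|noncentral t with n − 1 df| < t at 0.975)

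The result does not depend on δ or on the sign of m. The values of m and r are assumptions, since the documents give none. For n = 30 the critical t is 2.045. Example with r = 0.5 and m = 0.2: SD of change = 1.0, noncentrality = 0.2 × √30 = 1.095, coverage = 81.5%.

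| r | CI half-width (outcome SDs) | m = 0.1 | m = 0.2 | m = 0.3 |
|---|---|---|---|---|
| 0.3 | 0.442 | 92.7% | 85.4% | 73.1% |
| 0.5 | 0.373 | 91.7% | 81.5% | 64.5% |
| 0.7 | 0.289 | 89.5% | 72.3% | 46.4% |

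With all 33 dyads and r = 0.5 the values are 91.4%, 80.0% and 61.3%. With m = 0 coverage is 95%. More dyads or a higher correlation narrow the interval around the wrong quantity, so coverage falls.

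**If the figure were used for sizing.** The documents do not say that it will be. Suppose an observed change of 0.5 SD is taken as a between-arm effect (two-sided 5%, 80% power, 1:1), which gives 63 per arm. If 0.2 SD of the change was natural improvement, the true effect is 0.3 SD, power at 63 per arm is 39%, and 175 per arm are needed. This shows the inflating direction only.

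**Why SDs and correlations are needed as well.** The same 0.5 SD change divided by the SD of change is 0.42, 0.50 or 0.65 for r = 0.3, 0.5 or 0.7. A standardised change therefore cannot be interpreted without r. The SD of change can be recovered from a t-based interval and n. The baseline and follow-up SDs and the pre-post and within-dyad correlations cannot.

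**Precision of the added estimates at n = 30.**

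- SD: the 95% CI runs from √(29/45.72) = 0.80 to √(29/16.05) = 1.34 times the observed SD.
- Correlation, observed 0.5: Fisher z = 0.549 ± 1.96/√27, which gives 0.17 to 0.73.
- Retention of 30/33: the exact 95% CI is 76% to 98%.

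**The case against.** The strongest reply is that this is a wording point in a plan that is already hedged. The sentence speaks of exploring potential effect sizes, plans estimation rather than testing, and makes no efficacy claim. Phase 2 Outcomes already uses neutral language. The planned interval is valid for mean change, so the coverage figures measure a misreading, and their inputs are assumed. All of that is true, and it limits the weight of the point. It does not remove it. The stated purpose of the estimate is effect sizes for later work, so the reading is the one the plan itself supplies.

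A second reply is that the documentary support for natural change is thin: the Aim 1 recovery remark concerns interview timing, regression to the mean is only possible, and nothing describes caregivers' course. That also stands, and it is why no direction or size of bias is claimed. The argument needs only that natural change cannot be ruled out or measured in one arm.

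A third reply is that SDs and correlations are also affected if natural course varies between patients, which the wide entry window makes likely. They are untouched only by a uniform shift in the mean. But a future trial with the same entry window would carry that variation in both arms, so these remain relevant planning inputs.

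Finally, some of the request is already planned. The Measurement Plan table covers recruitment and completion of the session and monitoring, and testing of the outcome instruments. Outcome SDs, the correlations and follow-up survey retention are not named.

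**Conclusion.** The concern holds. As written, the plan uses uncontrolled within-group change to explore effect sizes, and that change cannot be separated from natural course in this design. How far it departs from the intervention effect is unknown, in direction as well as size. Under assumed natural changes of 0.1 to 0.3 SD and correlations of 0.3 to 0.7, with 30 dyads, the nominal 95% interval contains the intervention effect between 92.7% and 46.4% of the time. With no natural change it is correct at 95%.

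This is a matter of labelling and reporting in an exploratory analysis that is secondary to feasibility and acceptability. It does not affect the pilot's size or its main aims. It should be corrected because the results are meant to support a larger trial and the correction is cheap.

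**What to change.** Replace the effect-size sentence in the Aim 2 Data Management and Analysis paragraph with:

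> Average change from baseline to follow-up, with 95% CIs, will be reported separately for patients and caregivers as uncontrolled within-group change and will not be interpreted as an intervention effect size. To inform future trial planning, the pilot will estimate outcome SDs and SDs of change, baseline-to-follow-up and within-dyad correlations, and follow-up retention, with confidence intervals.

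This brings the paragraph into line with the neutral wording in Phase 2 Outcomes. It needs no control arm, extra dyads or new data, only a few more summaries of what is already collected, plus a count of completed follow-up surveys.

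The costs are a less favourable headline figure and planning inputs that are imprecise at about 30 dyads, which is why they should carry intervals. The pilot would still give no estimate of the intervention effect, which a single-arm study cannot supply.
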